### **10.2.1 Overview of Treatment-emergent Adverse Events**

A treatment-emergent adverse event overview table will be prepared including the number of subjects reporting an adverse event, the percentage of subjects with an adverse event, and the number of events reported, for the following categories:

- All adverse events
- Severe adverse events
- Adverse drug reactions
- Adverse events leading to discontinuation
- Serious adverse events
- Adverse events leading to death

An adverse drug reaction is an adverse event judged by the investigator to be related to IMP with a reasonable possibility.

### **10.2.2 Incidence of Adverse Events**

Treatment-emergent adverse events will be tabulated by system organ class (SOC) alphabetically and preferred term (PT) in decreasing order of frequency. The following will be presented: number of subjects reporting an adverse event, the percentage of subjects with an adverse event, and the number of events reported.

Summary tables will be produced for the following:

- All adverse events
- Adverse events by causality (reasonable possibility / no reasonable possibility)
- Adverse events leading to death
- Adverse events by intensity (mild / moderate / severe)
- Adverse drug reactions by intensity (mild / moderate / severe)
- Serious adverse events
- Adverse events leading to discontinuation
- Other significant adverse events
- Unexpected non-serious adverse drug reactions
- Adverse events with an incidence of  $\geq 5\%$  in any treatment group
- Non-serious adverse events with an incidence of  $\geq 5\%$  in any treatment group

### 10.3 OHSS

OHSS will be tabulated by classification (mild, moderate, severe) and grade (1, 2, 3, 4, 5).

#### **Early OHSS (Including OHSS of Moderate/Severe Grade) and/or Preventive Interventions for Early OHSS**

Early OHSS is defined as OHSS with onset  $\leq 9$  days after triggering of final follicular maturation. Note that this includes OHSS with onset before triggering and OHSS with onset during stimulation where triggering is not performed.

The following endpoints are defined:

- Subjects with early OHSS
- Subjects with early OHSS of moderate or severe grade
- Subjects with preventive interventions for early OHSS
- Subjects with early OHSS and/or preventive interventions for early OHSS
- Subjects with early OHSS of moderate or severe grade and/or preventive interventions for early OHSS

For each definition the proportion of subjects will be tabulated. Treatments will be compared using a logistic regression model with treatment and age stratum as factors. Treatment comparisons will be produced for the overall Pan-Asian trial population and for the Chinese population.

The risk of preventive interventions for early OHSS and/or early OHSS is related to the ovarian response potential. AMH is a well-established predictor of ovarian response to gonadotropin treatment and was confirmed to be the best endocrine marker of ovarian response to FE 999049 treatment in the phase 2 trial. Since FE 999049 is dosed based on AMH it is likely that the relationship between AMH and the risk of experiencing preventive interventions for early OHSS and/or early OHSS differs between FE 999049 and GONAL-F. To further explore this for each of the endpoints above, two different logistic regression models will be fitted assuming an increasing risk with increasing AMH with two nested models as follows:

Model 1:  $\text{LOGIT}(\pi) = \beta_0 + \beta_1 \cdot \ln(\text{AMH})$ ,  
where  $\pi$  denotes the risk and the  $\beta$ 's denotes the regression coefficients.

Model 2:  $\text{LOGIT}(\pi) = \beta_0 + \beta_1 \cdot \ln(\text{AMH}) + \beta_{2,i} + \beta_{3,i} \ln(\text{AMH})$ ,  
where  $i=1, 2$  indicates the two treatments. This is model 1 with addition of treatment and treatment-by- $\ln(\text{AMH})$  interaction terms.

The two models will be compared using the likelihood ratio test. Adjusted odds ratio estimates (comparing FE 999049 to GONAL-F) and associated 95% Wald confidence interval will be provided. A statistically significant improvement with model 2 compared to model 1 should be interpreted as a treatment difference in that the relationship between AMH and the risk of experiencing preventive interventions for early OHSS and/or early OHSS.

The estimated risks based on the models will be plotted as a function of AMH, i.e. overall and for each treatment group. The plots will include observed incidences for AMH-based subgroups of subjects. The adequacy of the model fits will be evaluated using the Hosmer-Lemeshow goodness-of-fit test and by examining how well the model fit describes the data in the plot.

It should be noted that the likelihood ratio test using two nested models above corresponds to a test of the contrast  $\beta_{2,1} = \beta_{2,2} = \beta_{3,1} = \beta_{3,2} = 0$  in model 2 above.

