### **Extreme Ovarian Response**

The analyses of extreme ovarian response will be performed using the following definitions of extreme ovarian response: <4 oocytes retrieved,  $\geq 15$  oocytes retrieved,  $\geq 20$  oocytes retrieved, <4 or  $\geq 15$  oocytes retrieved and <4 or  $\geq 20$  oocytes retrieved. Subjects with cycle cancellation due to poor ovarian response will be included as <4 oocytes retrieved. Subjects with cycle cancellation due to excessive ovarian response will be included as  $\geq 15$  and  $\geq 20$  oocytes retrieved.

For each definition the proportion of subjects with extreme ovarian response will be tabulated. Treatment groups will be compared using a logistic regression model with treatment and age group as factors. The possibility of an interaction will be tested. The difference between treatments will be reported as an odds ratio including 95% confidence interval and p-value for test of no treatment difference. If the expected number of observations is less than five in any of the cells in the contingency table then Fisher's exact test within strata will be used as alternative.

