### **Early OHSS (Including OHSS of Moderate/Severe Grade) and/or Preventive Interventions for Early OHSS**

OHSS will for each treatment group be tabulated by classification (mild, moderate, severe) and grade (1, 2, 3, 4, 5). Early OHSS is defined as OHSS with onset  $\leq 9$  days after triggering of final follicular maturation. Note that this includes OHSS with onset before triggering and OHSS with onset during stimulation where triggering is not performed.

This endpoint will be tabulated and analysed in a similar manner as the proportion of subjects with extreme ovarian response. The analysis will be performed for the proportion of subjects with early OHSS, the proportion of subjects with early OHSS of moderate or severe grade, the proportion of subjects with preventive interventions for early OHSS, the proportion of subjects with early OHSS and/or preventive interventions for early OHSS, and the proportion of subjects with early OHSS of moderate or severe grade and/or preventive interventions for early OHSS.

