#### 3.2 Determination of Sample Size

The primary objective of this trial is to demonstrate non-inferiority of FE 999049 compared with GONAL-F with respect to ongoing pregnancy rate in women undergoing controlled ovarian stimulation. The non-inferiority limit for the difference between treatments (FE 999049 versus GONAL-F) is -10.0% (absolute) for the primary endpoint.

Since this is a non-inferiority trial, the full analysis set (FAS) and the per-protocol (PP) analyses are equally important, i.e. non-inferiority should be established for both analysis sets in order to have a robust conclusion. Therefore, the expected proportion of subjects with major protocol deviations should be taken into account when setting the total sample size for the trial. The proportion of subjects with major protocol deviations is assumed to be at most 8%.

The trial is designed to have 90% power of achieving the primary objective for the overall Pan-Asian trial population and 80% power in the Chinese population. The number of subjects needed to achieve 90% power depends on the assumptions regarding the ongoing pregnancy rate. Based on an assumed ongoing pregnancy rate of 32.2% observed in the PP population of the ESTHER 1 trial, N=918 subjects are required in the PP population to obtain a power of 90%. Anticipating at most 8% major protocol deviations this results in N=1000 subjects to be randomised. The power is reasonably robust against deviations from the ongoing pregnancy rate assumption of 32.2%: a 35% ongoing pregnancy rate would still result in a 88.9% power, while lower rates will only increase the power (e.g. 30% yields 91.1% power). Recruiting at least 740

subjects in China is expected to secure that consistency can be established between the results from the overall Pan-Asian trial population and the Chinese trial population. In addition, to obtain approval in other Asian countries at least 260 subjects are needed. Thus a total sample size of 1,000 subjects will be recruited for this trial.

A blinded sample size reassessment will take place when data on the primary endpoint are available for 70% of the planned subjects or when 800 subjects are randomised, whichever comes first. The sample size reassessment will be done without breaking the blind and without inflating the type I error of the trial, in line with the current regulatory guidelines for non-inferiority trials by FDA and in general by EMA.

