## 9.3 Secondary Endpoints

For each secondary endpoint the analysis based on the FAS will be used to assess the statistical significance of differences between treatments. The analysis based on the PP analysis set will be considered supportive and should lead to a similar but not necessarily statistically significant result in order to have a robust interpretation.

Statistical tests will be performed using a two-sided test at a 5% significance level. Treatment differences will (where appropriate) be presented with 95% confidence intervals and p-values corresponding to the statistical test of the hypothesis of 'equal effect' against the alternative of 'different effect'.

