## **Ovarian Response and Extreme Ovarian Response**

The ovarian response will be defined based on the number of oocytes retrieved, and if the cycle was cancelled, the reason for cycle cancellation. Subjects will be grouped according to ovarian response as:

- Low response (<4 oocytes retrieved or cancellation of cycle due to poor ovarian response)
- Moderate response (4-7 oocytes retrieved)
- Targeted response (8-14 oocytes retrieved)
- Hyperresponse (15-19 oocytes retrieved)
- Severe hyperresponse ( $\geq 20$  oocytes retrieved or cancellation of cycle due to excessive ovarian response)

Extreme ovarian response will be defined as:

- <4 oocytes retrieved or cancellation of cycle due to poor ovarian response
- $\geq 15$  oocytes retrieved or cancellation of cycle due to excessive ovarian response
- $\geq 20$  oocytes retrieved or cancellation of cycle due to excessive ovarian response
- <4 or  $\geq 15$  oocytes retrieved or cancellation of cycle due to poor or excessive ovarian response
- <4 or  $\geq 20$  oocytes retrieved or cancellation of cycle due to poor or excessive ovarian response

For each definition of ovarian response and extreme ovarian response the proportion of subjects will be tabulated. Treatments will be compared using a logistic regression model with treatment and age stratum as factors. The difference between treatments will be reported as an odds ratio including 95% confidence interval and p-value for test of no treatment difference. If the expected number of observations is less than five in any of the cells in the contingency table then Fisher's exact test will be used as alternative. The possibility of a treatment-by-age interaction will be investigated.

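### SAP 10.3 gives the OHSS comparisons no small-count fallback, although the Protocol has one, so an arm with no events would leave the odds ratio and any Wald result unusable

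*SAP*

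**What the plan says.** **Protocol.** Section 9.7.3 (Extreme Ovarian Response) compares treatments by logistic regression with treatment and age group. If an expected cell count is below five, "then Fisher's exact test within strata will be used as alternative". The early OHSS paragraph adopts this: "This endpoint will be tabulated and analysed in a similar manner as the proportion of subjects with extreme ovarian response". The late OHSS paragraph refers back to early OHSS. Every OHSS endpoint in the Protocol therefore inherits the small-count rule.

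**SAP.** Section 9.3 keeps the rule for ovarian response without the within-strata wording: "then Fisher's exact test will be used as alternative". The cancellation endpoints in 9.3 refer back to it. Section 10.3 does not refer back. It states the early OHSS comparison afresh: "Treatments will be compared using a logistic regression model with treatment and age stratum as factors". No fallback follows. Late OHSS and combined OHSS are analysed like early OHSS, and the comparisons are made for the overall and the Chinese populations.

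Section 10.3 does not say whether the p-value of this age-adjusted model is Wald or likelihood-ratio. For a separate pair of AMH models on each OHSS endpoint it names a likelihood-ratio test and Wald intervals.

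SAP section 12 says that secondary analyses were clarified and some added. It does not mention the OHSS fallback.

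**The concern.** The small-count rule survives for ovarian response and cancellation but is missing for early and late moderate/severe OHSS, where sparse counts are most likely. The two documents now give different rules for the same endpoints.

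If one arm has no events, the maximum-likelihood estimate of the treatment log odds ratio runs off to infinity. Software stops at an arbitrary iteration and prints a huge standard error, a useless Wald interval and a Wald p-value near 1. The analyst must then pick another method after seeing the data, and the choice moves the p-value a long way.

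**Working it through.** **The plan's own figure.** The documents state no figure for OHSS. The design figure can be checked, which confirms the arm sizes used below. The SAP says "The trial is designed to have 90% power of achieving the primary objective", and also "The non-inferiority limit for the difference between treatments (FE 999049 versus GONAL-F) is -10.0% (absolute) for the primary endpoint". At the assumed rate of 32.2%, n per arm = (1.960 + 1.282)² × 2 × 0.322 × 0.678 / 0.10² = 459, so 918 in total, as stated. Then 918/0.92 = 998, stated as 1,000.

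**Inputs from the documents**
- 1:1 allocation and 1,000 subjects: 500 per arm.
- At least 740 in China: 370 per arm.
- Test level, from SAP 9.3: "Statistical tests will be performed using a two-sided test at a 5% significance level".
- Any OHSS with FE 999049 was reported as common, 1% to under 10% (Protocol 1.3).
- Preventive interventions with FE 999049 were half as frequent as with GONAL-F (Protocol 1.1).

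**Assumptions.** OHSS counts, OHSS rates by grade and age-stratum sizes (300/120/80 per arm) are not in the documents.

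**Step 1: how often the Protocol rule would apply.** With equal arms, the expected events per arm are half the total, so the trigger fires when total events are below 10. For equal true rates p, the chance is P(Bin(2n, p) ≤ 9):

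| Rate per arm | Overall (n = 500) | China (n = 370) |
|---|---|---|
| 0.5% | 97% | over 99% |
| 1% | 46% | 79% |
| 1.5% | 7% | 33% |

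**Step 2: one empty arm.** Take GONAL-F 4/1/1 by age stratum and FE 999049 0/0/0.
- Logistic model, Wald: log odds ratio −22.2, SE about 15,900, p = 0.999. Stopping the iteration earlier gives −15.7, SE 630, p = 0.98. Both are artefacts of where the fit stopped.
- Likelihood-ratio test of the same model: statistic 8.36, p = 0.004. Hand check: 2 × 6 × ln 2 = 8.32.
- Pooled Fisher: 2 × C(500,6)/C(1000,6) = 0.031. The exact age-stratified test also gives 0.031.
- Firth regression: odds ratio 0.08, p = 0.013.
- With 370 per arm the Wald (0.98 at the earlier stop), likelihood-ratio and Fisher p-values are the same to two significant figures.

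**Step 3: where it does not fail**
- Small but non-zero, 7 against 1: odds ratio 0.14, Wald p 0.067, Fisher 0.069.
- 9 against 1: Wald 0.036, Fisher 0.021.
- Empty oldest stratum, 9/3/0 against 2/1/0: odds ratio 0.245, Wald 0.030, Fisher 0.034. Only that stratum's own coefficient diverges.

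**Step 4: how likely the damaging case is.** Six events is the fewest that reach Fisher p < 0.05 against zero (five gives 0.062). The chance is (1 − p_FE)ⁿ × P(Bin(n, p_GF) ≥ 6):

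| GONAL-F rate | FE half, n = 500 | FE half, n = 370 | FE quarter, n = 500 | FE quarter, n = 370 |
|---|---|---|---|---|
| 0.5% | 1.2% | 0.5% | 2.2% | 0.7% |
| 1% | 3.1% | 2.6% | 11.0% | 6.7% |
| 2% | 0.6% | 1.8% | 7.6% | 11.7% |

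At equal rates of 0.5% and n = 500, the chance that either arm is empty while the other has at least six events is 0.7%.

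An empty FE 999049 arm by itself, which is enough to lose the odds ratio, is commoner. At FE 0.5% it is 0.995⁵⁰⁰ = 8% overall and 0.995³⁷⁰ = 16% in China. At FE 1%, the lower end of the range reported for any OHSS, it is 0.7% and 2.4%.

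**The case against.** The strongest reply is that little of practical weight is lost.

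- **The p-value near 1 needs a Wald test.** SAP 10.3 does not name one for this model, and the likelihood-ratio p on the same data is 0.004. The likelihood-ratio test planned for the AMH models covers every OHSS endpoint and should still register the imbalance. This stands as a limit on the claim. It does not rescue the odds ratio or a Wald interval, and the AMH-model odds ratio would also be non-estimable with an empty arm.
- **A difference would not be hidden.** A reader might infer that following the SAP could conceal a real imbalance. The documents do not support that: the SAP tabulates every OHSS endpoint and OHSS by grade, and the Protocol requires narratives for all moderate and severe cases. A split of 6 against 0 would be visible, and so would an absurd standard error.
- **Empty age strata are harmless.** A reader might also expect a stratum without events to break the treatment comparison. Step 3 shows that it does not.
- **Dropping the within-strata wording does no harm shown here.** In step 2 the Protocol's version gives three separate p-values (0.12, 1.00, 1.00) and no overall test, whereas pooled and stratified exact tests agree at 0.031.
- **These are secondary comparisons** without multiplicity adjustment.

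What remains is an unlisted divergence between the documents and a model with no usable estimate when an arm is empty.

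**Conclusion.** The concern holds in a limited form. SAP 10.3 omits the fallback that the Protocol gives all OHSS endpoints, and section 12 does not disclose it. The documents do not show whether this was intended.

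The failure requires exactly zero events in one arm. The odds ratio and Wald interval are then lost, and a Wald p-value is meaningless. On identical assumed data the reported p could be 0.999, 0.031 or 0.004 depending on a choice that the SAP leaves open. Exposure lies mainly in the moderate/severe endpoints and the China analysis. A zero FE 999049 arm together with enough GONAL-F events to be significant has a chance of roughly 0.5% to 12% under the assumed unequal rates. All of these probabilities rest on assumed OHSS rates.

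It would go too far to read this as a failure of logistic regression for rare events in general, or as a defect in the ovarian-response or cancellation analyses, which keep a fallback. The primary analysis is not touched.

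**What to change.** In SAP 10.3, add a rule for every OHSS endpoint, in both the overall and the Chinese population.

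- **Trigger:** any expected count below five in the treatment-by-outcome table, or an arm with no events. The second part is needed because 10 against 0 gives an expected count of exactly five, so the first part alone would not fire, yet the Wald p is 0.97 against a Fisher p of 0.002.
- **Method:** one named combined method replaces the maximum-likelihood Wald result. It can be an exact test (the Fisher rule already in SAP 9.3, or its age-stratified conditional version) or Firth logistic regression with treatment and age and profile-likelihood intervals. Choose one now. Restoring the Protocol's wording unchanged would not do, because it gives no overall test.
- **Disclosure:** list the change in SAP section 12.

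The cost is a few sentences and standard software options. An exact test is somewhat conservative: for 7 against 1, Fisher gives 0.069 where Firth gives 0.036. No change is needed to the primary analysis or to the ovarian-response and cancellation endpoints.

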### **Late OHSS (Including OHSS of Moderate/Severe Grade)**

Late OHSS is defined as OHSS with onset >9 days after triggering of final follicular maturation.

The following endpoints are defined:

- Subjects with late OHSS
- Subjects with late OHSS of moderate or severe grade

These endpoints will be tabulated and analysed in a similar manner as the endpoints defined for early OHSS.

### **OHSS (Early and/or Late) and/or Preventive Interventions for Early OHSS**

The following endpoints are defined:

- Subjects with early and/or late OHSS
- Subjects with early and/or late OHSS of moderate or severe grade
- Subjects with early and/or late OHSS and/or preventive interventions for early OHSS
- Subjects with early and/or late OHSS of moderate or severe grade and/or preventive interventions for early OHSS

These endpoints will be tabulated and analysed in a similar manner as the endpoints defined for early OHSS.

### **10.4 Safety Laboratory Variables**

Safety laboratory variables will be grouped under “Haematology” and “Clinical Chemistry”.

The baseline is based on the blood sample drawn at stimulation day 1. Treatment-emergent laboratory data will be obtained at end-of-stimulation and end-of-trial.

The circulating levels of clinical chemistry and haematology parameters including change from baseline will be tabulated for each time-point for each laboratory variable.

Shift tables will be prepared to compare baseline values to the end-of-stimulation and end-of-trial values, using a categorisation of low, normal and high values at each visit. Low, normal and high will be defined according to the reference ranges provided by the central laboratory.

Summary tables by visit will be prepared displaying the proportion of subjects who have a markedly abnormal value. These tables will also include a break-down by classification of the baseline value. Markedly abnormal criteria for the safety laboratory variables is specified in Appendix 1.

All laboratory values will be listed by subject and time point. Values outside the reference range and markedly abnormal values will be flagged.

### **10.5 Injection Site Reactions**

Injection site reactions will be tabulated by symptom (redness, pain, itching, swelling, bruising), time after injection (immediately after, 30 minutes after, 24 hours after) and intensity (none, mild, moderate, severe, moderate/severe).

### **10.6 Treatment-induced Anti-FSH Antibodies**

The proportion of subjects with treatment-induced anti-FSH antibodies as well as the proportion of subjects with treatment-induced anti-FSH antibodies with neutralising capacity will be tabulated. Furthermore, for subjects with treatment-induced anti-FSH antibodies, all antibody assessments will be listed.

### **10.7 Immune-related Adverse Events**

Potential immune-related adverse events will be tabulated by SOC and PT using the SMQs for: anaphylactic reaction, angioedema, hypersensitivity reactions and severe cutaneous reactions and the Ferring defined PTs including: asthenia, pyrexia, body temperature increased, chills, influenza-like illness, musculoskeletal pain, syncope and pre-syncope.

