### **7.2.22 Immune-related Adverse Events**

All adverse events reported in the trial will be analysed to identify those that potentially are immune-related. To identify all possible cases, a broad-scope search on Standardised Medical Dictionary for Regulatory Activities (MedDRA) Queries (SMQs), including 'Hypersensitivity', 'Anaphylactic reactions', 'Angioedema' and 'Severe cutaneous adverse reactions' will be considered. Moreover, to identify the potential cases manifested by non-specific symptoms and not covered by these SMQs, other MedDRA PTs like 'Musculoskeletal pain', 'Asthenia', 'Pyrexia', 'Chills', 'Body temperature increased', 'Influenza like illness', 'Injection related reaction', 'Pre-syncope' and 'Syncope' will also be taken into account. Hypersensitivity reactions manifested by local symptoms will be identified using the MedDRA high level term (HLT) 'injection site reactions'. The SMQs may include very specific as well as less specific terms; hence a narrow-scope search on these SMQs will be carried out to identify those cases that are highly likely to represent an immune-related aetiology.

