### **Immune-related Adverse Events**

Potential immune-related adverse events will be tabulated using the SMQs, PTs and HLTs mentioned in section 7.2.22.

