#### Secondary Endpoints

- Positive  $\beta$ hCG rate (positive serum  $\beta$ hCG test 13-15 days after transfer)
- Clinical pregnancy rate (at least one gestational sac 5-6 weeks after transfer)
- Vital pregnancy rate (at least one intrauterine gestational sac with fetal heart beat 5-6 weeks after transfer)
- Implantation rate (number of gestational sacs 5-6 weeks after transfer divided by number of embryos transferred)
- Ongoing implantation rate (number of intrauterine viable fetuses 10-11 weeks after transfer divided by number of embryos transferred)
- Proportion of subjects with extreme ovarian responses, defined as  $<4$ ,  $\geq 15$  or  $\geq 20$  oocytes retrieved
- Proportion of subjects with early OHSS (including OHSS of moderate/severe grade) and/or preventive interventions for early OHSS

- Proportion of subjects with cycle cancellation due to poor or excessive ovarian response or embryo transfer cancellation due to excessive ovarian response / OHSS risk
- Number and size of follicles on stimulation day 6 and end-of-stimulation
- Number of oocytes retrieved and proportion of subjects with <4, 4-7, 8-14, 15-19 and ≥20 oocytes retrieved
- Percentage of metaphase II oocytes (only applicable for those inseminated using ICSI), fertilisation rate as well as number and quality of embryos on day 3 after oocyte retrieval
- Circulating concentrations of LH, estradiol, progesterone, inhibin A and inhibin B on stimulation day 6 and end-of-stimulation
- Circulating concentrations of FSH on stimulation day 6, end-of-stimulation and oocyte retrieval as well as FSH population pharmacokinetic parameters
- Total gonadotropin dose and number of stimulation days
- Proportion of subjects with investigator-requested gonadotropin dose adjustments
- Frequency and intensity of adverse events
- Changes in circulating levels of clinical chemistry and haematology parameters and proportion of subjects with markedly abnormal changes
- Frequency and intensity of injection site reactions (redness, pain, itching, swelling and bruising) assessed by the subject during the stimulation period
- Proportion of subjects with treatment-induced anti-FSH antibodies, overall as well as with neutralising capacity
- Frequency and intensity of immune-related adverse events
- Proportion of subjects with cycle cancellations due to an adverse event, including immune-related adverse events, or due to technical malfunctions of the administration pen

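### SAP 10.7 searches for immune-related adverse events with fewer terms than protocol 7.2.22 specifies, and SAP section 12 does not declare the difference

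*SAP*

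**What the plan says.** The endpoint carries the same name in both documents: "Frequency and intensity of immune-related adverse events" (SAP section 2.2, Secondary Endpoints).

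Protocol section 7.2.22 builds the search from four parts:

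- a broad-scope SMQ search, "including 'Hypersensitivity', 'Anaphylactic reactions', 'Angioedema' and 'Severe cutaneous adverse reactions' will be considered";
- preferred terms for non-specific symptoms, a list that ends "Influenza like illness', 'Injection related reaction', 'Pre-syncope' and 'Syncope' will also be taken into account";
- a high level term for local reactions: "Hypersensitivity reactions manifested by local symptoms will be identified using the MedDRA high level term (HLT) 'injection site reactions";
- a second pass, in which "a narrow-scope search on these SMQs will be carried out to identify those cases that are highly likely to represent an immune-related aetiology".

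Protocol section 9.7.3 turns this into the analysis instruction: "Potential immune-related adverse events will be tabulated using the SMQs, PTs and HLTs mentioned in section 7.2.22".

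SAP section 10.7 tabulates by SOC and PT. Its sources are the same four SMQs and "the Ferring defined PTs including: asthenia, pyrexia, body temperature increased, chills, influenza-like illness, musculoskeletal pain, syncope and pre-syncope". It does not refer back to protocol 7.2.22.

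**The concern.** The SAP is the document that governs the analysis. Its section 10.7 reads as a complete recipe for this endpoint, but it differs from the protocol's recipe. Running it as written applies a narrower case definition than the protocol's to a named secondary safety endpoint.

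The part left out has a purpose of its own. The protocol uses the high level term to find hypersensitivity that shows itself locally. Under protocol section 8.3.2, injection-site reactions to the IMP enter the adverse event data only if they lead to discontinuation, further investigation or treatment. The IMP reactions that the high level term would return are therefore the ones that someone had to act on. Evaluating immunogenicity is a stated secondary objective, and this table is the clinical companion to the antibody results.

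**Working it through.** No arithmetic applies beyond counting terms. The two definitions compare as follows.

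| Element | Protocol 7.2.22 and 9.7.3 | SAP 10.7 |
|---|---|---|
| SMQs | 4 | the same 4 |
| SMQ scope | broad, then narrow | not stated |
| Named preferred terms | 9 | 8 |
| High level terms | 1 ('injection site reactions') | 0 |
| Intensity for this subset | in the endpoint name only | in the endpoint name only |

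**Preferred terms.** The protocol names musculoskeletal pain, asthenia, pyrexia, chills, body temperature increased, influenza like illness, injection related reaction, pre-syncope and syncope, which makes 9. The SAP names all of these except injection related reaction: 9 − 1 = 8. The SAP list opens with the word 'including' and the protocol list with 'like', so neither is strictly closed. The ninth term is unnamed in the SAP, not excluded.

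**High level term.** The openness of the SAP list extends to preferred terms only. It cannot bring in a high level term, and no other part of SAP 10.7 does.

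**Effect on the count.**

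- Leaving out the high level term can lower the number of cases found.
- Leaving out the preferred term can lower it too, but less certainly, because the list is open.
- Not mentioning the narrow search does not lower the count if the broad search is run: the narrow search picks out a more specific subset of the same SMQ cases. What is lost is that subset, and the reader is not told which scope was used.
- Lack of an intensity breakdown removes a display and no cases.

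**What remains visible elsewhere.** SAP 10.2.2 tabulates all treatment-emergent adverse events by SOC and PT, and also by causality, by intensity, if serious and if leading to discontinuation. SAP 10.5 tabulates injection-site reactions by symptom, time and intensity. SAP 10.6 covers antibodies. None of these identifies immune-related events as a group, and the intensity tables in 10.2.2 cover all adverse events and adverse drug reactions, not this subset.

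**Declaration.** SAP section 12 names two deletions: the sensitivity analyses in subjects with oocytes retrieved or with transfer, and the ordinal-data analyses. For secondary endpoints it otherwise speaks of clarification and additions. The reduced immune-related search is not mentioned.

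**Size.** The documents give no rate for these terms as adverse events, so the shortfall cannot be computed. For IMP reactions it is probably small, given the restriction in protocol 8.3.2 and the low incidence of generally mild local reactions reported in protocol section 1.3. Local reactions to NIMPs are not restricted in this way. They are reported whenever they meet the adverse event definition, and the high level term would return those as well.

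**The case against.** The strongest reply is that little is lost. The events are still recorded and appear in the general adverse event tables. The endpoint is descriptive and has no bearing on the non-inferiority claim. Both preferred-term lists are illustrative. Some local hypersensitivity terms may already fall inside the hypersensitivity SMQ, which cannot be settled without MedDRA. SAP section 14 places the table shells in a separate document, and these may hold the full term list.

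Most of this stands, and it sets the size of the point. It does not remove the mismatch: protocol 9.7.3 calls for the high level terms, SAP 10.7 has none, and an unseen shell is no substitute for a definition in the plan.

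A reader might go further and infer that four departures from the protocol mean the endpoint will be under-counted. The documents do not support that. Only the high level term, and less certainly the one preferred term, can lower the count. Nor does the SAP drop an intensity table that the protocol's analysis text had planned: protocol 9.7.3 asks for none for this subset, so the gap is shared by both documents and section 12 had nothing to declare on it. A reader might also infer that managed injection-site reactions vanish from the safety evaluation. They do not; what they could lose is their place in this one table.

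**Conclusion.** Wrong as written, minor. SAP 10.7 omits the one high level term that the protocol requires, leaves one of nine preferred terms unnamed, and states no SMQ scope where the protocol calls for two. Section 12 declares none of this. The immune-related table could therefore miss injection-site reactions that needed active management, and it would lack the narrow-scope subset. The intensity half of the endpoint's name has no planned table in either document.

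This conclusion assumes that SAP 10.7 is followed literally and that the separate shells do not already restore the protocol's terms. It has no effect on the primary analysis, the sample size or data collection.

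**What to change.** In SAP 10.7:

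1. Add the high level term 'injection site reactions' and the preferred term 'Injection related reaction', preferably by citing protocol 7.2.22 and fixing the term list before unblinding.
2. State the SMQ scope and tabulate broad and narrow results separately.
3. Add intensity to the table so that it matches the endpoint's name.

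If the shorter search is deliberate, declare and justify it in SAP section 12 instead. The cost is a few lines of SAP text, a search-term list and one extended table; no new data are needed.
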